3.10. Outcome measures

Questionnaires

Pre-screened: For pre-screening the 20-item self-report measure that assesses the 20 DSM-5 symptoms of PTSD. The measure is commonly used to screen for PTSD and has been used in a similar pilot study in Egypt [72]. It has also been validated in an Arabic-speaking country [71]. Please see Section 3.7 procedure for pre-screening process.

For clinical outcomes: The ITQ will be used for the assessment of CPTSD symptoms. The ITQ assesses 12 symptoms (6 for post-traumatic stress disorder and another 6 for disturbances in self-organisation). A diagnosis of CPTSD requires the endorsement of at least one of the two symptoms from each of the three PTSD symptom clusters described above (i.e., re-experiencing in the here and now, avoidance, and sense of current threat) and at least one of the two symptoms from each of the three Disturbances in Self-Organisation (DSO) clusters (i.e. affective dysregulation, negative self-concept, and

disturbances in relationships). Items are scored on a Likert scale ranging from 0 (not at all) to 4 (extremely). The endorsement of a symptom item is defined as a score ≥ 2 .

We will also include assessment tools measuring other relevant secondary outcomes, using culturally validated assessments such as the Patient Health Questionnaire (PHQ-9) [73] for depression. The PHQ-9 score may range from 0 to 27, since each of the 9 items can be scored from 0 (not at all) to 3 (nearly every day). Higher scores mean higher levels of depression. We will use the General Anxiety Disorder Questionnaire (GAD-7) [74] for anxiety. The GAD-7 score may range from 0 to 21, since each of the 7 items can be scored from 0 (not at all) to 3 (nearly every day). Higher scores mean higher levels of anxiety. For somatic symptoms we will use the Somatic Symptoms Scale (SSS-8). The SSS-8 score may range from 0 to 32, since each of the 8 items can be scored from 0 (not at all) to 4 (severely). Higher scores mean higher levels of somatic symptoms [SSS-8, 75]. Finally, for well-being we will use the WHO-5 Wellbeing Index [76]. Scores range from 0-25, based on a Likert scale from 0 (not at all) to 5 (all of the time) for each item. Higher scores reflect better levels of well-being.

All measures have been validated in Arabic speaking samples. We will collect demographic information (e.g., sex, age, religion, education, occupation, income) from participants for possible correlations. Please find all questionnaires in English and Arabic in Appendix 7.

Qualitative feedback interviews

For acceptability outcomes: We will conduct feedback qualitative interviews after each module and overall feedback on therapy process at the end of therapy. Participants are asked about their experiences with the content and implementation process of the manual. As an example, Interview template for Module 1 and 2 can be found in appendix 8.

3.11. Data Analysis

Statistical analysis plan

For primary outcomes: We will primarily assess feasibility by determining the percentage of participants who complete the study until the end (among those who sign the informed consent). Based on reported dropout rates from studies using similar modular interventions with trauma survivors, we will consider 80-90% participation and adherence as excellent, 70-80% as satisfactory, and 60-70% as acceptable [42, 77].

We will assess the ITI feasibility, using the same method based on the percentage of participants who complete the ITI; 80-90% participation and adherence is considered as excellent, 70-80% as satisfactory, and 60-70% as acceptable.

In addition, we will calculate the mean and standard deviation of completion rates to offer more detail into the variation in adherence.

For secondary outcomes: Descriptive statistics will be calculated for demographic information and baseline characteristics of participants. For clinical outcomes, we will analyze changes in PTSD symptomatology and other clinical outcomes (e.g., depression, anxiety, somatic symptoms, and well-being) at the four or five measurement points depending on group allocation. (See section 3.8 procedures). We will use intermediate assessments after each module to statistically describe the participants' state (means, standard deviations, correlations), enhancing our understanding of the effects of intervention components.

Next, we will use pre-post comparisons based on data from the first and last assessments to establish the status of change (clinically significant change) for each participant. We will conduct one-

sided paired measures Student's t-tests at the group level. The null hypothesis (H0) is that the change is zero. The alternative hypothesis (H1) is there will be a decrease in symptoms of CPTSD, depression, anxiety, and somatization; and an increase in rates of wellbeing. Student's t tests will be conducted with a significance level of 0.05. If the assumptions for the Student's t test are not satisfied, we will utilize non-parametric tests, specifically the Wilcoxon test for paired measurements.

We will perform longitudinal analyses utilizing multilevel linear models. This will enable us to gain a deeper understanding of how participants' progress throughout the duration of psychotherapy. The multilevel models will enable us to examine the impact of additional variables, such as gender, type of trauma, or group allocation (i.e., number of sessions), in an exploratory manner.

Considering our limited sample size of 20 participants and the fact that similar interventions have shown an effect size of 0.24, we acknowledge that the lack of statistical power may prevent us from observing the effects of our intervention on clinical outcomes.

Statistics will be conducted by the same team that conducted the analysis of the parallel Swiss arm of the study (see Section 3.2 Research Team) and will be facilitated by the free software R [78]

Qualitative analysis

We will use framework analysis to extract the most important information related to acceptability from patient and therapists qualitative interviews [79]. We will use MAXQDA software to facilitate analysis [80]. Data will be transcribed and translated in Arabic by the applicant and research assistants, who are native speakers.

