3.6. Target population

Our target population is Egyptian adults living in urban settings, i.e., major cities in Egypt. Egypt is a large, heavily populated, and diverse country, challenges encountered by urban populations may significantly differ from those faced in rural areas. Literature from LMIC show that urban environments are characterized by increased violence rates and limited healthcare resources [67]. As we aim to have our diagnostic module and therapeutic manual to be culturally and structurally sensitive, we thought that focusing on urban population will allow us to include more contextual variables thereby making the intervention more targeted and relevant.

The adapted manual will be piloted with 20 participants. We aim to recruit an equal number of male and female participants. However, this number may change since women seek help more than men in Egypt [68]. Given that the project is time-bound due to funding reasons and the progression of this PhD project, recruitment should be concluded by August 2024. This short time frame might limit our ability to make extra efforts to include additional male participants.

Patients are included if they are 18 years of age or older, can give written or oral consent, are literate, have a history of severe and/or prolonged trauma, and screen positive for CPTSD. The therapeutic program will take place in Cairo, however participants are allowed to join if they reside in any other major city, if they wish. They will be excluded if they present an imminent risk of suicide, psychotic symptoms, and/or severe alcohol and/or drug abuse, or have been in therapy before (i.e., completed more than 5-10 sessions of psychotherapy).

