3.8. Pilot study procedures

Recruitment & prescreening

Our sample will be recruited from multiple settings, including referrals from MHPs in private and public settings, social media outlets, via calls for participation through university announcements, and local NGOs.

Participant will be recruited using a convenience sampling strategy [69]. Given the sensitivity of this population exposed to violence and potentially associated stigma, convenience sampling might facilitate recruitment. More importantly convenience sampling is recommended in such exploratory projects to ensure flexibility needed to make ‘real-time judgements’ during fieldwork regarding changes needed in sample characteristics or size [70].

Participants will be contacted by the applicant for phone prescreening call. Ethical guidelines recommend that phone prescreening may be conducted to determine specific inclusion and exclusion criteria and is allowed before obtaining consent. We use phone screening, for the purpose of not wasting participant’s time, and given transportation difficulties in Cairo. During the phone screening call, participants will be:

- introduced to the researcher.
- told how long the phone call is expected to take.
- informed that a set of questions will be asked to determine eligibility of the nature and sensitivity of the questions.
- asked whether there might be a better time for them to answer these questions.
- If they agree to conduct the phone call at this moment or suggested another time to be re-contacted, they will be asked if they had experienced violence for a long period of time.
- pre-screened on the phone using the PCL-5, which consists of 20 PCL-5, a diagnostic tool with 20-items to assesses the symptoms of PTSD (See Section 3.10 Outcome measures). A score above 23 suggested a provisional diagnosis of PTSD in another Arabic-speaking sample [71]. No additional identifying information will be asked and no official record of scores will be kept or connected to the participant in anyway. The same procedure was conducted in another pilot study in a trauma-focused online therapy program in Egypt [72]. Participants who score over 23 will be sent the consent sheet via the contact information they provided and invited for a study information and screening session.

Screening & informed consent

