Screening interviews will be conducted by the applicant (NH), who is also a psychotherapist and practices under the licence of Maadi Psychology Center in Cairo, Egypt. During this interview additional inclusion criteria questions (i.e., immediate risk of suicide, acute psychosis, severe alcohol, or drug abuse) will be asked. Additionally, participants will be asked if they have been in therapy before or are currently in therapy. If patients are not eligible or do not want to participate, they will be referred to other treatment pathways and public and private facilities in Cairo. We have provided a list of available and trusted service providers or facilities (emergency services and outpatient services; please see Appendix 6).

NH will then explain the study information in detail and respond to the participants’ questions. This part of the session will resemble an “onboarding session,” in which the content of the manual and the study procedures will be explained more in detail. They will be informed that if they participate in the study, they will receive a standardized group therapy following a manual that includes 18-25 sessions. They will be informed of the study design, and the difference between therapy sessions and assessment

and feedback sessions. Please see below sections of procedures details. They will also be notified that therapy is provided at no cost and that their time for feedback interviews will be compensated. (For more information on compensation, please see below). They will be informed about their voluntary participation and the possibility of withdrawal at any time.

If the participant still agrees to participate, they will be asked to sign the informed consent form. Please see Appendix 2 for consent forms. As per guidelines, the participant would have had time to read the consent form sent to them prior to coming to the screening session to have more than 24 hours before consenting. We will retain the consent form as part of the study records.

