Participants will then be asked to fill self-report questionnaires. Please see Section 3.10 for outcome measures. Patients will be given the option to either complete the self-report questionnaires themselves, or, if they prefer to have the therapist read the items to them. If the participant screens positive for CPTSD using the ITQ. They will then be informed that they are eligible and asked to join our study. If they agree to join, we will collect socio-demographic data, i.e., sex, age, religion, marital status, education, occupation, income.

Participants will receive compensation of 700 EGP for this session.

Cultural module-ITI pilot

At the end of this interview, patients who have screened positive for CPTSD will be asked if they are interested in participating in two formulation sessions to pilot the ITI and the cultural and structural module (please see Section 3.5). This question will be asked to participants whether they are interested in joining our therapy program or not. These sessions will be conducted independently of the screening and therapy process. Participants will be informed that their decision will not impact their inclusion in the therapeutic program and will be reminded that they have the right to decline. They will be reminded about their voluntary participation and the possibility of withdrawal at any time. They will be given a separate consent sheet and will also be informed that their time will be compensated. Please see appendix 2 for consent forms.

NH will conduct the ITI (original version and additional items of the cultural and structural module), to assess the feasibility and cultural applicability of the added module. She will be trained along with the UniL team to conduct the clinical interview. ITI formulation sessions will be audio recorded for research purposes. We will record sessions to use them to collect idioms of distress, free-listed symptoms, and cultural norms as a part of the ethnopsychological portion of this study, which will allow us to further adapt the diagnostic module and the therapy in the future. We did not conduct interviews with patients during the formative research phase (only mental health professionals, and family members/close ones of individuals exposed to violence). This was due to the high vulnerability of our population, as it would have been unethical to cause distress through interview questions without providing a treatment option.

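### The therapy feasibility rate counts everyone who signs consent, but consent is signed before the ITQ settles eligibility, so people who cannot enter therapy count as non-completers

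*Combined protocol and SAP*

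**What the plan says.** Section 3.11 defines the main feasibility measure for the therapy by "determining the percentage of participants who complete the study until the end (among those who sign the informed consent". It grades the result as excellent at 80 to 90%, satisfactory at 70 to 80% and acceptable at 60 to 70%, and says these bands come from dropout rates in studies of similar modular treatments.

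Section 3.6 lists who may enter. Among other things they must "have a history of severe and/or prolonged trauma, and screen positive for CPTSD".

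Section 3.8 gives the order of steps:

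1. Phone prescreen with the PCL-5: "Participants who score over 23 will be sent the consent sheet" and are invited to a screening session.
2. At that session, before any signature: "During this interview additional inclusion criteria questions (i.e., immediate risk of suicide, acute psychosis, severe alcohol, or drug abuse) will be asked". Previous and current therapy are asked about at the same point.
3. After the study has been explained: "If the participant still agrees to participate, they will be asked to sign the informed consent form".
4. "Participants will then be asked to fill self-report questionnaires". These include the ITQ.
5. For those who screen positive on the ITQ: "They will then be informed that they are eligible and asked to join our study".

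The diagnostic interview (ITI) pilot is offered only to people with a positive screen, and it has its own consent: "They will be given a separate consent sheet and will also be informed that their time will be compensated".

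**The concern.** The event that defines the denominator (signing) comes before a test that decides eligibility (the ITQ). Someone who signs and then screens negative is not invited to join, so cannot complete the study. The definition in Section 3.11 still counts that person among those who should have completed.

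Such people are to be expected. The PCL-5 used before consent covers DSM-5 PTSD symptoms. The ITQ rule in Section 3.10 also requires a symptom in each of the three clusters of disturbances in self-organisation, which the PCL-5 cut-off does not test. A person can pass the first and fail the second.

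Feasibility is a primary outcome, and the bands are drawn from treatment dropout. An ITQ-negative signer has neither dropped out nor failed to adhere. The label given to the therapy could therefore fall because of how the screen performed. If the denominator is chosen only once the counts are known, that choice is post hoc.

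**Working it through.** The plan states no expected feasibility rate, so there is no figure to reproduce. The check has two parts: the order of steps, and the arithmetic of the denominator.

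**Order of steps.** Sections 3.8 and 3.6 together give: PCL-5 by phone; suicide, psychosis, substance and prior-therapy questions; signature; ITQ; invitation to join. The ITQ is the only eligibility step described after the signature. No section removes ITQ-negative signers from the Section 3.11 denominator, and the main text describes only one consent for the therapy study. The ITI rate is unaffected, because that pilot starts after a positive ITQ and has a separate consent.

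**Inputs.** Planned number in therapy: 20 (Section 3.6). Bands: Section 3.11. Number of ITQ-negative signers, *e*: not given, so assumed to be 0 to 5. For this first calculation, assume that exactly 20 join, with no decliners and no replacements.

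**Formula.** Literal rate = completers / (20 + *e*). Since *e* enters only the denominator, the rate can only fall.

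| Completers | e=0 | e=1 | e=2 | e=3 | e=4 | e=5 |
|---|---|---|---|---|---|---|
| 20 | 100.0% | 95.2% | 90.9% | 87.0% | 83.3% | 80.0% |
| 17 | 85.0% | 81.0% | 77.3% | 73.9% | 70.8% | 68.0% |
| 16 | 80.0% | 76.2% | 72.7% | 69.6% | 66.7% | 64.0% |
| 15 | 75.0% | 71.4% | 68.2% | 65.2% | 62.5% | 60.0% |

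The first row is also the ITQ-positive yield, 20/(20 + *e*). With perfect retention, the graded rate would simply report how the screen performed.

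**When the label changes.** The rate falls below an edge *t* when *e* > completers/*t* − 20.

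- 17 completers, 80% edge: 17/0.80 − 20 = 1.25, so *e* = 2 (77.3%, excellent to satisfactory).
- 17 completers, 70% edge: 17/0.70 − 20 = 4.29, so *e* = 5 (68.0%, acceptable).
- 15 completers, 70% edge: 15/0.70 − 20 = 1.43, so *e* = 2 (68.2%, satisfactory to acceptable).
- 16 completers, which starts on the 80% edge, 70% edge: 16/0.70 − 20 = 2.86, so *e* = 3 (69.6%).

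From mid-band (17 or 15 completers), one ITQ-negative signer changes nothing and two change the label. Two among 22 signers is a yield of 20/22 = 90.9%.

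**Precision.** Exact (Clopper-Pearson) 95% intervals are 62.1% to 96.8% for 17/20 and 54.6% to 92.2% for 17/22. For 15/20 they are 50.9% to 91.3%, and for 15/22 they are 45.1% to 86.1%. They are wide whichever denominator is used.

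**The case against.** **The word participants may mean those enrolled.** People are asked to join only after a positive ITQ, the manual is to be piloted with 20 participants, and Section 3.12 ties dropout to withdrawal from the intervention. On that reading an ITQ-negative signer was never in the study. The reading is possible, but Section 3.8 also uses the word for people still being screened, and the parenthesis in Section 3.11 names consent signers outright. The consent forms in Appendix 2 are not visible and might clarify the intention. If enrolled participants were meant, the sentence still needs changing, because two analysts could report different primary results from the same data.

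**The bands may not require a therapy-only denominator.** Section 3.11 labels them as covering participation as well as adherence, and the denominators in the cited dropout studies cannot be seen. This supports keeping eligible people who decline. It does not support counting people the protocol itself excludes.

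**The repair keeps some people who never start therapy.** Eligible decliners and early leavers replaced under Section 3.9 remain as non-completers, and a denominator of joiners would also be defensible. That choice is partly judgement. Keeping them stays closest to the plan's consent-based rule and avoids flattering the therapy; reporting completion among joiners alongside it covers the alternative.

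**Age and literacy.** The documents do not say when these two criteria are checked. That stands, but it does not alter the position of the ITQ.

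**Size.** The number of ITQ-negative signers is unknown, and zero or one would leave both mid-band labels unchanged. That also stands, and it limits how serious the point is.

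**Conclusion.** The concern holds. Followed as written, the Section 3.11 rule counts people who fail an inclusion criterion as non-completers in a primary outcome, and the bias runs in one direction.

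The size rests on assumed counts: with 20 joining and no decliners or replacements, two ITQ-negative signers lower the mid-band labels by one step (85.0% to 77.3%, or 75.0% to 68.2%). The actual effect depends on an ITQ-positive yield that the documents do not give.

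This should be fixed but is not grave. The bands are descriptive, Section 11 sets no threshold for moving to the randomised trial, the rate can be recomputed later, and the wide intervals make any label weak evidence.

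**What to change.** In Section 3.11, define the graded therapy rate as completers divided by consented participants who screen ITQ-positive. State that eligible people who decline to join, and early leavers replaced under Section 3.9, stay in the denominator as non-completers.

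Report three further rates without a grade: ITQ-positive among consented (screening yield), joined among ITQ-positive (uptake), and completers among joined (retention).

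An example with assumed counts: 26 sign, 4 are ITQ-negative, 22 are ITQ-positive, 1 declines, 21 join, 1 of those leaves early and is replaced within the 21, and 17 complete.

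| Rate | Result |
|---|---|
| Literal rule, completers/signers | 17/26 = 65.4% (acceptable) |
| Proposed graded rate | 17/22 = 77.3% (satisfactory) |
| Screening yield, ungraded | 22/26 = 84.6% |
| Uptake, ungraded | 21/22 = 95.5% |
| Completers among joined, ungraded | 17/21 = 81.0% |

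As a separate drafting tidy-up, make the bands non-overlapping, since 70% and 80% each fall in two of them.

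The cost is one sentence and three more descriptive rates, all from counts the study already collects.

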Therapists and RAs costs are covered by the Prix CADOT funding. MA-level therapists in training cannot be paid as their work will count towards the hours they need to fulfill in their degree.

We provide below two tables with the weekly progression plans of the pilot study:

3 module plan:

Week	0	1	2-6	6	7-12	12	13-17	18	19
Visit	Study information & pre-assessment	Introduction session	Module 1	Intermediate assessment 1/Feedback	Module 2	Intermediate assessment 2/Feedback	Module 3	Final Session	Post-assessment/Feedback

4 module plan:

Week	0	1	2-6	6	7-12	12	13-17	17	18-24	25	26
Visit	Study information & pre-assessment	Introductory session	Module 1	Intermediate assessment 1/Feedback	Module 2	Intermediate assessment 2/Feedback	Module 3	Intermediate assessment 3/Feedback	Module 4 (individual therapy)	Final session	Post-assessment/Feedback

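### The ITQ that makes a person eligible also appears to be the ITQ baseline, so part of any fall in ITQ score is expected without a treatment effect

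*Combined protocol and SAP*

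**What the plan says.** The point rests on five places read together, because no single sentence states it.

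- Section 3.8, recruitment: people over the PCL-5 telephone cut-off are "invited for a study information and screening session".
- Section 3.8, screening and consent: at that session, after consent, "Participants will then be asked to fill self-report questionnaires", with a pointer to the outcome measures. Eligibility follows from the same forms: "If the participant screens positive for CPTSD using the ITQ".
- Section 3.8, weekly tables: both schedules show one visit before the introductory session, at week 0, labelled "Study information & pre-assessment".
- Section 3.10: the ITQ is also the CPTSD outcome measure.
- Section 3.11: "we will use pre-post comparisons based on data from the first and last assessments to establish the status of change". The test is a one-sided paired t-test at 0.05 (Wilcoxon if assumptions fail), and "The null hypothesis (H0) is that the change is zero". Each participant is also to be given a clinically significant change status.

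Section 3.11 counts four measurement points for participants on three modules and five for those on four. Pre, two intermediate and post make four; pre, three intermediate and post make five. That leaves no second ITQ before therapy. Section 3.8 mentions baseline assessments in July and August but does not separate them from screening.

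**The concern.** An ITQ score is a stable level plus fluctuation on the day. Admitting only those who score positive on one occasion favours people whose fluctuation was upward that day. At the last assessment the fluctuation is fresh, so the mean falls even if nobody has changed. Zero is then not the no-effect value for this contrast, and the shift favours the alternative hypothesis.

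At stake are the secondary ITQ result and the individual change status, both of which start from the selected reading. Initial impact on clinical outcomes is a stated aim in Section 2, intended to inform later validation. The caution about power in Section 3.11 concerns missing an effect; this bias runs the other way.

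**Working it through.** **The plan's own figure.** There is none to reproduce: the documents give no power calculation and no allowance for regression to the mean.

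**Inputs from the documents.** n = 20; one-sided alpha 0.05; first minus last assessment; null value zero; ITQ item endorsed at 2 or more on a 0 to 4 scale, with at least one of two items needed in each of six clusters (Section 3.10).

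**Inputs assumed.** Retest correlation r = 0.7 to 0.9, and share p of those screened who are ITQ-positive = 50 to 90%. The documents give neither. True change is set to zero.

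**Expected fall.** With a normal score in SD units of the screened population and cut-off c such that a share p lies above it:

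fall = (1 − r) × φ(c)/p

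For p = 50%, c = 0 and φ(c)/p = 0.399/0.5 = 0.798, so r = 0.7 gives 0.3 × 0.798 = 0.239 SD. For p = 80%, φ(c)/p = 0.280/0.8 = 0.350, giving 0.105 SD. For p = 90%, φ(c)/p = 0.1755/0.9 = 0.195, giving 0.058 SD.

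**Rejection rate.** The baseline variance after selection is v = 1 + cλ − λ², with λ = φ(c)/p. The SD of the difference is √[(1 − r)²v + 1 − r²]. For p = 50% and r = 0.7, v = 0.363 and the SD is √(0.09 × 0.363 + 0.51) = 0.737. The standardised fall is 0.239/0.737 = 0.325, and the noncentrality is 0.325 × √20 = 1.45. A noncentral t on 19 degrees of freedom exceeds the critical value 1.729 with probability 0.40.

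| ITQ-positive | Fall in SD, r = 0.7 / 0.8 / 0.9 | Rejection rate, r = 0.7 / 0.8 / 0.9 |
|---|---|---|
| 50% | 0.239 / 0.160 / 0.080 | 0.404 / 0.301 / 0.194 |
| 80% | 0.105 / 0.070 / 0.035 | 0.149 / 0.124 / 0.096 |
| 90% | 0.058 / 0.039 / 0.019 | 0.095 / 0.085 / 0.073 |

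Simulation of the same model agrees within 0.003. With 14 to 16 completers the rates are 8.5 to 34% (50 to 80% positive) and 7 to 9% (90% positive). The telephone PCL-5 step is left out. Including it needs an assumed pass rate and correlation with the ITQ, and raises the rates somewhat (8 to 11% at 90% positive among those who pass).

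**Item-level check.** Twelve items were simulated with the six-cluster rule and no true change, at a total-score retest correlation of about 0.63 to 0.82; impairment items were not modelled.

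- About 47% positive: mean fall 1.3 to 2.6 points on 0 to 48, rejection 27 to 45%, and 27 to 34% of screen-positives no longer meet the rule at retest.
- About 79% positive: 0.6 to 1.1 points, 12 to 17%, and 12 to 15%.

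The loss of positive status matters only if change is judged by diagnosis. The plan does not define clinically significant change.

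**What a second pre-treatment reading would do.** If the fluctuations at screening and week 1 have correlation k, the remaining fall is k(1 − r)φ(c)/p. For p = 50% and r = 0.7 this is 0 at k = 0, 0.120 SD at k = 0.5 and 0.191 SD at k = 0.8. Across r = 0.7 to 0.9 and 50 to 80% positive, rejection is about 5%, 7 to 17% and 8 to 29% respectively.

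**The case against.** The strongest reply is that Section 3.1 already calls the study uncontrolled and rules out efficacy conclusions, and that regression to the mean is one of the things a missing control leaves open. This stands as a limit on importance. It does not dispose of the point: that section cites lack of control and power, not selection on the baseline, while Section 3.11 still plans a one-sided test against zero and an individual change status. This component can also be reduced without a control group.

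The second reply is that the size is wholly assumed. That is correct. Referral, reported prolonged violence and the PCL-5 step make a high positive share plausible, and at 90% the test is close to nominal. The upper figures need r = 0.7 and only half of those screened to be positive.

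The third is that a separate pre-treatment ITQ may exist. None is described; if there is one, the plan should say which ITQ counts as first.

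Three stronger readings are tempting and not supported:

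- A reader might set the fall beside the plan's statement that "similar interventions have shown an effect size of 0.24" and infer that the artefact rivals the expected effect. The plan does not say how that figure is standardised or whether it is a pre-post or a between-group effect, so the two cannot be compared.
- A reader might infer that all five questionnaires are equally biased. Only the ITQ is used for selection at that session; the other four are affected less, through any fluctuation they share with it that day.
- A reader might infer that the study's main conclusions fail. The primary outcomes are feasibility and acceptability, which do not use this contrast.

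**Conclusion.** The concern holds for one secondary outcome. As the documents read, the ITQ change and the individual change status start from a reading selected for being high, so some apparent improvement is expected with no treatment effect. Under assumed retest correlations of 0.7 to 0.9 and n = 20, the nominal 5% test rejects about 10 to 40% of the time if 50 to 80% of those screened are ITQ-positive, and about 7 to 10% if 90% are. The true size may be near nominal and cannot be settled from the documents. The change is worth making because it is specific and cheap, not because a primary conclusion depends on it. Confidence is medium, since the single-ITQ reading is an inference from several sections.

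**What to change.** 1. Add to Section 3.11: *The screening ITQ is used for eligibility only. The ITQ pre value is a repeat completed at the start of the week-1 introductory session, before any session content. If it is missing, the screening value is used and flagged, and results are shown with and without those participants.* The fallback keeps someone who misses that repeat from being dropped under the complete-pairs rule in Section 3.12. The other four questionnaires may keep their week-0 values.
2. Report mean change with a 95% confidence interval beside the planned tests. As a check with no added burden, report ITQ change from intermediate assessment 1 onward, noting that it omits module 1.
3. State that this reduces but does not remove regression to the mean, and does not replace a control group. If baselines are already collected, state the bias as a limitation of the ITQ change and of the individual change status.

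**Cost.** Twelve symptom items repeated per participant at an existing session. Section 3.8 lets participants choose "if they prefer to have the therapist read the items to them", which needs arranging privately in a group setting. The team must settle whether the 700 EGP assessment payment applies and whether Section 4.4 calls for an ethics submission. Correction is only partial if the two readings share fluctuation. The gap between them may run from days to about seven weeks (1 July to 18 August is 48 days), and a short gap makes a high correlation more plausible.

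**Optional and minor.** Include therapy group in the planned multilevel model as a sensitivity analysis, since modules 1 to 3 are delivered in four groups of five. Four groups give only a rough estimate of clustering.
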